13.3. RANDOMISATION

Each subject will receive a screening number as soon as site staff enters the IWRS, after they have signed the ICF (Visit 1).

The screening number will consist of country number (1 digit), a site number (3 digits) and a continuous number for a subject at an individual site (3 digits), e.g. 1001001. Every subject who signs the ICF must be entered into the IWRS system regardless of eligibility.

At Visit 2, eligible subjects will be randomised using the IWRS according to a pre-specified randomisation scheme such that they either receive NAC or ambroxol hydrochloride or placebo.

The randomisation within each site will be done with blocks sized of unequal length to guarantee a good balance among NAC, ambroxol hydrochloride and placebo at any stage of the enrolment minimizing the procedure selection bias.

The allocation to the treatment will be stored within the IWRS database until unblinding of the trial is requested. Unblinding may be performed directly by the Investigators only in case of SAE of life-threatening significance where knowledge of treatment assignment is essential for the future management of patient care (see [Section 15.1](#)).

13.4. INVESTIGATIONAL MEDICINAL PRODUCT ACCOUNTABILITY

IMP inventory and accountability records will be maintained within IWRS. The following rules are to be followed:

- a) The Investigator will keep IMPs in a pharmacy, or a locked and secure storage facility, accessible only to those individuals authorised by the Investigator to dispense the IMPs.
- b) The inventory will be maintained by the Investigator or pharmacist or other nominated individual. The inventory will be done by means of a specific "Subject/Study Investigational Product Accountability Record & Investigational Product Reconciliation Log" and will include details of IMPs received and a clear record of when they were dispensed.
- c) At the conclusion or termination of the clinical trial, the Investigator will conduct a final IMP inventory and to record the results of the inventory on an Investigational Product Return Form. The monitor will check that IMP accountability was correctly performed. The Investigator will return all original IMP containers, whether empty or full, to the CRO for final reconciliation and destruction.
- d) The Investigator/pharmacist agree not to supply IMP to any person except those named as Investigators/Co-Investigators as detailed in the Site Signature/Delegation Log, and to subjects in this trial.

For instructions to maintain the study patient and rater-blind, see [Section 4](#).

14. CLINICAL TRIAL AMENDMENTS

Changes to the CTP can be made preparing written amendments to be agreed and signed by the Principal Investigator and Sponsor. No substantial amendment can be implemented without a favourable opinion of the Ethics Committee (EC) and Competent Authority (CA) and CA, unless the changes consist of urgent safety measures to protect trial subjects.

Amendments which are non-substantial amendments as defined by current regulations can be sent to EC/CA for notification as applicable per local requirements and may be implemented at the site before EC notification according to local rules.

15. DEVIATIONS FROM THE CLINICAL TRIAL PROTOCOL

Any major or critical deviation which may have an impact on study results and/or the safety of the subjects should be immediately reported to the CRO and a decision will be taken together with the Sponsor whether or not the patient for whom the deviation from the CTP took place is to continue in the trial. A deviation log will be maintained to track actual deviations and decisions taken. All deviations will be reported to the EC and CA according to ICH-GCP and local requirements.

In case of an emergency deviation from the CTP has to be implemented for a give patient, this deviation will be only applied to that individual.

In such an emergency the Investigator must contact the CRO by telephone as soon as possible.

15.1. CODE BREAKING

The code for any individual subject will not be broken by the Investigator/rater during course of the trial except in the circumstance of an SAE where knowledge of treatment assignment is essential for the future management of patient care.

Despite the fact that this study is not double-blind, in order to ensure proper documentation, in case of emergency, unblinding of the treatment is to be done through IWRS. The IWRS will be designed to send a confirmation (by fax and/or notification email) to the site for every transaction performed by the site users. Site users will be provided with usernames and passwords to access the IWRS. Unblinding of the study treatment must be done in case of an emergency situation, where the Investigator/rater considers it essential to know what treatment the subject was taking. Access to the unblinding option will be granted only to the Investigators and sub-Investigators at the sites. The IWRS will promptly notify the Sponsor and the Clinical Trial Monitor whenever a treatment code is unblinded. If the treatment code has been opened, this must be recorded in the eCRF.

Users from PAREXEL and Sponsor Pharmacovigilance will have their own passwords to unblind subjects in case of suspected unexpected serious adverse reactions (SUSARs) to be reported to the CA and ECs.

16. CLINICAL TRIAL WITHDRAWALS/DROP-OUTS

Patients will be withdrawn from the trial for one of the following reasons:

- patient may withdraw from the study at any time at his/her own request;
- patient may withdraw from the study due to an AE;
- patient may be withdrawn at any time at the discretion of the Investigator for safety, behavioural, compliance or administrative reasons;
- patient may be withdrawn due to lack of adherence to study medication regimen.
- Female patient who becomes pregnant should be withdrawn from the trial and followed-up in accordance with [Section 18.8](#);
- Patient should be withdrawn from the trial once rescue mucolytic is received;
- non-emergency unblinding of study treatment allocation;
- lost to follow up: before a subject is deemed lost to follow up, the Investigator or designee must make every effort to regain contact with the participant (where possible, 3 telephone calls and, if necessary, a certified letter to the participant's last known mailing address or local equivalent methods). These contact attempts should be documented in the participant's medical record. Should the participant continue to be unreachable, he/she will be considered to have withdrawn from the study;

The sponsor, CA, or EC/IRB(s), can terminate the trial or participation of an individual site.

The reason for removal of a subject from the trial or premature discontinuation of treatment must be fully documented in the eCRF as well as in respective source documents. Follow-up for withdrawn subjects follows the procedures described in [Section 18.8](#) and [Section 18.9](#).

17. STOPPING AND DISCONTINUATION CRITERIA FOR THE TRIAL

The trial may be prematurely terminated or placed on temporary hold for the following reasons:

- the Sponsor feels that the number and/or severity of AEs justifies discontinuation of the trial;
- the Sponsor considers the applied doses of one or more IMPs to be no longer relevant;
- data not known before, become available and raise concern about the safety of one or more IMPs so that continuation would pose potential risks to the subjects;

Premature termination of the trial must be reported to the EC and CA according to applicable laws generally within 30 days. A detailed written explanation of the reason should be given and alternative procedures for subjects under treatment specified.

However, trial results have to be reported according to the requirements outlined in this CTP as far as applicable.

If, after the termination of the trial, the risk/benefit analyses have changed, the new evaluation should be provided in case it will have an impact on the planned follow-up of the patients who have participated in the trial. If possible, the patients should return to the clinic for an early End of Treatment Visit.

18. REPORTING SAFETY INFORMATION

18.1. DEFINITION OF ADVERSE EVENT

An AE is "any untoward medical occurrence in a patient or clinical trial subject administered a medicinal product and which does not necessarily have a causal relationship with this treatment".

AEs include:

- worsening (change in nature, severity or frequency) of conditions present at the onset of the trial;
 - worsening of expectoration difficulties and related symptoms may prompt discontinuation of the patient and immediate administration of rescue mucolytic if judged to be in the patient's best interest by the investigator and/or the patient him/herself
- subject deterioration due to the primary illness;
- intercurrent illnesses;
- drug interactions;
- events related or possibly related to concomitant medications;
- abnormal laboratory values, as well as significant shifts from baseline within the range of normal, which the Investigator considers to be clinically significant.

An AE can therefore be any unfavourable and unintended sign (including an abnormal laboratory finding), symptom, or disease temporally associated with the use of an investigational medicinal product, whether or not considered related to the IMP.

An unscheduled Deterioration Visit should be conducted whenever possible ([Section 10.10](#)).

18.2. DEFINITION OF ADVERSE EVENT OF SPECIAL INTEREST

No AEs of special interest are defined for this trial.

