5. EVALUATION OF THE ANTICIPATED RISKS/BENEFIT RATIO

NAC has been available to patients as a mucolytic agent for many years and has a well-established and satisfactory safety and tolerability profile (see IB).

Independently of route of administration (inhalation, oral, intravenous) adverse events are reported rarely following NAC administration and are usually mild and transient.

The most frequent adverse events associated with NAC oral administration are gastrointestinal (e.g., vomiting, diarrhoea, stomatitis, abdominal pain and nausea). Hypersensitivity reactions (e.g. anaphylactoid reactions, urticaria, rash, pruritus, and bronchospasm) have been reported less frequently after oral administration, while with the IV administration they were reported more frequently compared to gastrointestinal symptoms. Some of the hypersensitivity reactions were associated to higher infusion rate. Most anaphylactoid reactions can be managed by temporarily suspending the acetylcysteine infusion, administering appropriate supportive care. A cumulative analysis of all safety reports received by the Sponsor up to September 2017 for NAC IV, confirmed the nature and severity of the events were in line with the above profile of the product.

Intravenous NAC has been studied in clinical trials and published case series both as mucolytic agent and as an antidote against intoxication by paracetamol and other toxic agents including amanita phalloides and chlorinated hydrocarbons. Overall, in published studies in humans, a total of 745 patients were exposed to iv NAC at doses ranging from 500 mg/day to 980mg/kg/day for a duration of 1 to 18 days. Details of safety results are included in the IB.

In published studies, whereas iv NAC as mucolytic agent typically was given at doses up to 1000 mg/day, much higher iv doses of NAC as antidote were given over multiple days, maintaining a satisfactory safety profile.

Locatelli and colleagues (19) published two case series, one of 86 patients with acute intoxication from amanita phalloides and the other of 35 patients with acute intoxication from chlorinated hydrocarbons. Patients received iv NAC 300 mg/kg/day for 3 to 14 days and 3 to 18 days respectively. The safety and tolerability profile were overall benign, with 4 out of 121 exposed patients suffering from anaphylactoid reaction or rash (due to the rapid administration of the bolus

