20.4.8. SAFETY DATA

All safety endpoints will be summarised and analysed using the Safety Population.

Incidence of Treatment Emergent Adverse Events

The number and the percentage of subjects reporting TEAEs, treatment emergent SAEs, severe TEAEs, TEAEs leading to discontinuation and TEAEs leading to death will be presented by treatment group, along with the number of events occurring.

TEAEs will be summarised also by System Organ Class and Preferred Term according to MedDRA; they will be additionally summarised by severity and relationship to treatment. A separate summary table will be provided for SAEs.

Only TEAEs, i.e. events with an onset date on or after the date of IMP start, will be included in the summary tables. Individual data listings will include all AEs recorded; a separate listing will be provided for treatment-emergent SAEs.

Vital Signs

Descriptive statistics for vital signs will be presented overall and by treatment.

Physical examination data

Descriptive statistics for physical examination data will be presented overall and by treatment.

Haematology and clinical chemistry

Haematology and clinical chemistry tests results will be converted to standard international units and summarised by treatment group using descriptive statistics for continuous variables. Summaries for change from Visit 1 will be also provided. Frequency of subjects with values appearing outside the central laboratory normal range will be reported by visit for each treatment group. All values appearing outside the laboratory normal range will be highlighted in listings.

12-lead Electrocardiogram

Descriptive statistics for ECG results will be presented overall and by treatment (normal, abnormal clinically non-significant, abnormal clinically significant).

Adherence and Exposure

Subject adherence will be summarised by treatment group presenting descriptive statistics and percentages of adherent subjects, i.e. with a least 80% of compliance.

The total number of doses of IMP taken by each subject, will be summarised as well.

If an AE has a partial or fully missing date, and it is unclear whether the AE is treatment-emergent, it will be assumed that it is. In the AEs analysis, when relationship to study drug is missing for a treatment-emergent adverse event it will be imputed to be drug related. More detail will be provided in the Statistical Analysis Plan (SAP).

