If used during pregnancy, caution is advised.

Breast-feeding

There are no studies showing whether or not acetylcysteine passes into breast milk.

Effects on ability to drive and use machines

Effects on the ability to drive or operate machinery has not been studied.

Undesirable effects

The most common undesirable effects described in the literature regarding the acetylcysteine administered intravenously are skin rash, urticaria and pruritus, and they most commonly occur during administration of the initial bolus.

In a randomised, open multi-centre study, during the first 2 hours after i.v. administration of acetylcysteine, the following undesirable effects occurred:

Immune system disorders

Very common: anaphylactoid reaction (17%).

Cardiac disorders

Common: Tachycardia.

Respiratory, thoracic and mediastinal disorders *Uncommon:* Pharyngitis, rhinorrhoea, rhoncus, bronchospasm.

Gastrointestinal disorders

Common: Vomiting (11%), nausea.

Skin and subcutaneous tissue disorders *Common:* Pruritus, skin rash.

Vascular disorders

Common: Facial flushing.

The following undesirable effects have been reported based on long-term post-marketing experience and their frequency can not be estimated from the available data.

Local administration

Immune system disorders: Hypersensitivity reaction.

Respiratory, thoracic and mediastinal disorders: Bronchospasm, rhinorrhoea.

Gastrointestinal disorders: Stomatitis, vomiting, nausea.

Skin and subcutaneous tissue disorders: Angioedema, urticaria, rash, itching.

Systemic administration (high dose i.v. administration)

Immune system disorders: Anaphylactic shock, anaphylactic/anaphylactoid reactions, hypersensitivity reaction.

Cardiac disorders: Tachycardia.

Respiratory, thoracic and mediastinal disorders: Bronchospasm, dyspnoea.

Gastrointestinal disorders: Vomiting, nausea.

Skin and subcutaneous tissue disorders: Angioedema, urticaria, facial flushing, rash, itching.

General disorders and administration site conditions: Face oedema.

Investigations: blood pressure decreased, prothrombin time prolonged.

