4.10.2 Adverse Events

An AE is "any untoward medical occurrence in a patient or clinical trial subject administered a medicinal product and which does not necessarily have a causal relationship with this treatment".

Adverse events will be coded using Medical Dictionary for Regulatory Activities (MedDRA) Version 23.1.

Any AE occurring onset date on or after the date of the first IMP administration, i.e. Visit 2, until the end of the trial, i.e. follow-up phone call, will be considered as a treatment emergent AE (TEAE). AEs which are already present before the first IP and increase in severity after the first IP will be considered as TEAEs. Pre-existing AEs before the first IP with no increase in severity after the first IP will not be considered as TEAEs. A Pre-treatment AE will be defined as any AE with an onset date before the date of first administration of IMP.

Imputation of partial dates of AE record is described in Appendix 4.14 (section 4.14.7).

Following summaries will be provided:

- An overview of all TEAEs including any TEAEs with relationship to IMP, any TEAEs leading to drug withdrawn, any TEAEs leading to drug interrupted, any TEAEs leading to fatal, any TEAEs of Covid-19, by treatment group.
- A summary of Pre-treatment Adverse Events by SOC, PT and CTCAE Grade (Safety Set)
- A summary of the number and percentage of subjects reporting an TEAE and the number of TEAEs, by treatment group, SOC, and PT
- A summary of the number and percentage of subjects reporting a TEAE with Incidence $\geq 5\%$ of Patients by treatment group, SOC, and PT
- A summary of the number and percentage of subjects reporting Other adverse events with Incidence $\geq 5\%$ of Patients by treatment group, SOC, and PT
- A summary of the number and percentage of subjects reporting a TEAE Related to IMP by treatment group, SOC, and PT

- A summary of the number and percentage of subjects reporting an TEAE and the number of TEAEs, by treatment group, relationship, SOC, and PT
- A summary of the number and percentage of subjects reporting an TEAE and the number of TEAEs, by treatment group, severity, SOC, and PT
- A summary of the number and percentage of subjects reporting a TEAE Leading to Study Discontinuation by treatment group, SOC, and PT
- A summary of the number and percentage of subjects reporting a TEAE Leading to Drug withdrawal of IMP by treatment group, SOC, and PT

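### Hypersensitivity is the iv NAC risk that the protocol itself names, but no planned table counts patients with any such reaction or gives a between-arm difference

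*Protocol*

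**What the plan says.** Protocol section 5 names the reactions: anaphylactoid reactions, urticaria, rash, pruritus and bronchospasm. They were seen less often with oral NAC, "while with the IV administration they were reported more frequently compared to gastrointestinal symptoms". Two reference rates are given. Section 5 cites case series at 300 mg/kg/day "with 4 out of 121 exposed patients suffering from anaphylactoid reaction or rash". The NAC product information in Protocol Appendix 2 lists anaphylactoid reaction as very common, at 17%, in an open randomised study over the first two hours after iv dosing; dose and indication are not stated.

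Protocol 18.2 says "No AEs of special interest are defined for this trial", and 18.9.2 adds no reporting provision. Protocol 20.4.8 says that "TEAEs will be summarised also by System Organ Class and Preferred Term according to MedDRA", with further summaries by severity and relationship. SAP 4.10.2 lists the main TEAE table by arm, SOC and PT without a threshold. It adds a table of "subjects reporting a TEAE with Incidence" of at least 5%, and tables for related events, severity, study discontinuation and drug withdrawal. A subject is counted once per SOC and once per PT. SAP 4.10.7 gives a confidence interval for the proportion with a SUSAR; no other safety proportion has one.

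**The concern.** The safety objective is to confirm that iv NAC is safe and well tolerated, in a trial meant to be pivotal for registration in China. The natural safety question is how many patients in each arm had a hypersensitivity reaction, and the planned tables do not answer it. Under the headings of the appended product information, the five named reactions fall into three SOCs: immune, skin and respiratory. Adding rows does not recover the count, because one patient can appear in several.

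The existing summaries fill the gap only in part. Bronchospasm shares its SOC with events of the respiratory illness that every patient has. The related-event tables rest on causality judgement, and Protocol 10.2 describes the staff responsible for dosing, patient care and routine assessments as unblinded. The one safety interval covers reactions not identified in the reference safety information. If the Investigator Brochure lists hypersensitivity, that interval would largely leave this risk out; the brochure is not among the documents, so this stays conditional. A grouping chosen after unblinding would be open to the charge of being data-driven.

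**Working it through.** **Plan's own figures.** 100/(1 − 0.10) = 111.1, taken as 111 per arm and 333 in total, as stated. The efficacy powers also reproduce: 93.8% (Mann-Whitney) or 94.5% (t-type) against about 93% stated for superiority, and 81-82% against 82% for non-inferiority. The documents give no power or precision figure for hypersensitivity.

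**Inputs from the documents.** 111 per arm; a low reference rate of 4/121 = 3.3%; a high reference rate of 17%.

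**Assumptions, not in the documents.** Placebo rate 1%; events split equally over five PTs; 60% of events in the largest SOC. The 60% matches three of the five named reactions (urticaria, rash, pruritus) falling in the skin SOC under the product information's headings. Each row is assumed to hold hypersensitivity events only.

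**Rates compared.** For a grouped NAC rate p:
- grouped row: p against 1%
- largest SOC row: 0.6p against 0.6%
- single PT row: p/5 against 0.2%

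At p = 10% the expected NAC patients are 0.10 × 111 = 11.1 grouped, 0.06 × 111 = 6.7 in the SOC row and 0.02 × 111 = 2.2 in one PT row.

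**Yardstick.** Power = Σ Bin(x; 111, p₁) · Bin(y; 111, p₀) over all x > y with two-sided Fisher p ≤ 0.05. The plan has no safety test; this only puts the rows on one scale. The 5% table needs 0.05 × 111 = 5.55, so at least 6 patients. The chance for any of five PTs is 1 − (1 − q)⁵, treating PTs as independent, where q is the chance for one PT.

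| NAC rate | Grouped | Largest SOC | Single PT | Any of 5 PTs in the 5% table | Largest SOC row shows more on NAC than placebo |
|---|---|---|---|---|---|
| 3.3% | 7% | 1% | <0.1% | 0.1% | 73% |
| 5% | 24% | 7% | 0.1% | 0.5% | 87% |
| 8% | 64% | 29% | 0.7% | 4.5% | 97% |
| 10% | 83% | 48% | 2% | 12% | 99% |
| 17% | 99.6% | 90% | 15% | 62% | about 100% |

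**Sensitivity.** With a three-way PT split, single-PT power at 10% is 12% instead of 2%. With 2% on placebo and 17% on NAC, grouped power is 98% and largest-SOC power 81%. With 100 per arm, the figures at 10% are 77%, 40% and 1%.

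**What a grouped row would report.** At 10% against 1%, the standard error of the difference is √(0.10 × 0.90/111 + 0.01 × 0.99/111) = 0.030, so 9.0 points with a simple 95% interval of about 3.1 to 14.9. At 5% against 1% it is √(0.05 × 0.95/111 + 0.01 × 0.99/111) = 0.0227, so 4.0 points, about −0.5 to 8.5.

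**The case against.** The strongest reply is that nothing is hidden. The main TEAE table has no threshold, SOC rows are already counts of patients, and there are tables by relationship, severity, discontinuation and withdrawal, plus SAE tables and full listings. Judged by eye, the largest SOC row would show more NAC than placebo patients with probability 87% at a 5% rate and 99% at 10%. The safety objective is descriptive, no safety test is claimed, and a grouped count could be made from coded data at any time. Section 5 also says that adverse events with NAC are rare and usually mild and transient, and expects a small safety risk. All of this stands, and it limits the point to a missing summary.

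Two stronger readings are tempting. A reader might infer that these reactions are analysed only as scattered preferred terms, so that an excess would rarely show. The documents do not support this: SOC rows exist, and very small chances apply only to single PTs or to the supplementary 5% table at low to moderate rates. A reader might also count five or more SOCs. That requires adding facial flushing and tachycardia, which the product information lists as separate effects; the reactions named in section 5 fall in three.

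The reply does not remove the core gap. No row counts each affected patient once across SOCs, and seeing a higher number on NAC is weaker than a difference with an interval.

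**Conclusion.** The point holds as a cheap improvement. The plan names a main iv risk and then pre-specifies neither a patient-level count of it nor a between-arm difference. The gain from grouping is concentrated at NAC rates of about 5-10%, between the two reference rates in the protocol. At 10% against 1%, grouped power is 83%, against 48% for the largest SOC row and 2% for a single PT. Near 3.3%, even the grouped count has only 7% power, so grouping does not rescue detection. At 17% the largest SOC row already has 90%. These figures rest on the assumed 1% placebo rate, the 60% SOC share and the equal five-way PT split. The efficacy conclusions are not affected, and the documents do not support a claim that the safety tables would conceal an excess.

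**What to change.** In SAP 4.10.2, before unblinding, fix one list of preferred terms (or a standardised MedDRA query) for hypersensitivity and infusion reactions. Tabulate by arm the subjects with at least one such TEAE, each counted once. Give NAC-placebo and NAC-ambroxol risk differences with 95% confidence intervals, labelled descriptive and without a significance claim; a score-type interval suits the small counts. Refer to this group in Protocol 18.2. The adverse event data are already collected, so the cost is agreeing the list with pharmacovigilance and producing one extra table.
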